- m: In the imaging subgroup only, amyloid PET imaging will be conducted on or within 10 days after the scheduled Visits 29 and 42 (12 and 18 months). For those subjects who also consent to CSF assessment in addition to PET, CSF should be collected 2 to 4 days after study drug infusion at Visit 29, and the amyloid PET procedure should be scheduled to take place on a separate day within 10 days of Visit 29, but after CSF collection. (revised per protocol Amendment 06) For those subjects who did not consent to the imaging substudy in the Core Study, a baseline scan can be taken at Visit 42 (Week 79). Subjects who consented to the imaging subgroup in the Core Study may continue into the OLE if they re-consent. (revised per Amendments 08 and 11).
- n: Subjects may be given the option to receive home infusions during the Core Study (per DSMB charter, if allowed and conducted according to country and local guidelines; home infusions will not be allowed in Germany) for study drug administration during Visits 13, 14, and 15, and Visits 17 through 21, Visits 23 through 28, Visits 30 through 34, and Visits 36 through 40, inclusive, provided they express no clinical features related to drug infusion during the first 4 months of the study. Upon implementation of Amendment 07 newly enrolled subjects will not be offered the option for home infusions during the Core Study. Subjects opting for home infusions before the implementation of Amendment 07 will be allowed to continue with home infusions for the duration of their participation in the Core Study. (revised per Amendments 01, 03, 07, and 14)
- o: At Visit 3, blood will be taken for the BAN2401 assay approximately 4 hours after the end of infusion (before subjects leave the clinic for home). Subjects must stay in clinic for the full 4 hours following infusion during this first infusion visit. Subjects must stay in clinic for at least 2 hours following infusion up through Week 13 (Visit 9). After the Week 13 (Visit 9) Visit, if no untoward effects of infusion are noted, or infusion reactions can be prevented with prophylaxis, then subjects may be discharged from clinic 30 min after the end of infusion if judged medically stable by the investigator. At Visits 9, 16, 22, 29, 35, and 41, blood will be taken for the BAN2401 assay both predose and at least 2 hours after the end of infusion (before subjects leave the clinic for home). Subjects are required to remain in clinic for at least 2 hours following infusion at visits where PK samples are taken (except Visit 3, the first infusion visit). PK samples should be taken at least 2 hours after the end of infusion. These samples can be taken any time after those 2 hours and should generally be taken just prior to the subject leaving the site. (revised per Amendment 01) For subjects who participate in the CSF sub-study, serum PK sample should also be taken immediately following the CSF collection that is to take place 2 to 4 days after study drug infusion at Visit 29. For the same CSF sub-study subjects, the CSF sample should be taken predose at Visit 41 and the predose serum PK sample at Visit 41 should be taken immediately after the CSF sampling. (revised per Amendments 06 and 07)
- p: Blood for the BAN2401 anti-drug antibody assay will be taken as follows: predose at Visits 3, 9, 16, 22, 29, 35, and 42, and the Follow-Up Visit (Visit 43). Blood for the BAN2401 anti-drug antibody assay will also be taken at the Early Termination Visit when applicable.
- q: Those subjects who consent to CSF assessments should have CSF drawn via LP 2 to 4 days after the scheduled study Visit 29 (12 months) infusion, and serum PK samples should be taken immediately following the CSF collection. CSF samples should be collected predose on the day of the Visit 41 infusion. (revised per Amendment 06)

9.5.2.2 Total Volume of Blood and CSF

Table 9 presents the number of blood and CSF samples and the total volume of blood and CSF that will be collected throughout the Core Study. Additional samples may be taken at the discretion of the investigator if the results of any tests fall outside reference ranges or if clinical symptoms necessitate testing to ensure subject safety.

Table 9 Summary of Blood and CSF Sample Volumes

Assessment	Total number of collection time points	Sample volume, number of time points x volume per collection (mL)		Total volume (mL)
		Screening and Baseline Periods	Treatment and Follow-Up Periods	
Clinical laboratory tests	13	2 x 12 mL	11 x 10 mL	134 mL
Blood sampling for serum anti-BAN2401	8	-	8 x 10 mL	80 mL
Blood sampling for serum BAN2401 PK	13	--	13 x 3 mL	39 mL
APOE4 pharmacogenomics	1	1 x 6 mL	None	6 mL
Blood for exploratory biomarker analysis	3	1 x 6 mL	2 x 6 mL	18 mL
All blood samples, total volume collected				277 mL
CSF sampling	3	1 x up to 12 mL	2 x up to 12 mL	Up to 36 mL

APOE4 = apolipoprotein e4 variant, CSF = cerebrospinal fluid, PG = pharmacogenomic, PK = pharmacokinetic

9.5.3 Appropriateness of Measurements

All clinical assessments are standard measurements commonly used in studies of Alzheimer’s disease. The appropriateness of the Composite Clinical Score as an efficacy assessment is explained in [Section 7.2.1](#).

Standard safety assessments incorporated into this protocol include vital signs, clinical laboratory assessments, physical examinations, ECG measurements, and reports of AEs. Amyloid-related imaging abnormalities (ARIAs) that have been associated with related therapeutic interventions in AD are readily detected by MRI as planned for this study, in accordance with FDA guidelines.

The anti-BAN2401 assay was developed under the FDA guidance for detecting ADAs, and criteria for evaluating human samples have been developed using a preclinical (rabbit) positive control. The assay is run under GLP.

The C-SSRS has been endorsed by the FDA as a measure of potential suicidality.³⁶

9.5.4 Reporting of Serious Adverse Events, Pregnancy, and Other Events of Interest

9.5.4.1 Reporting of Serious Adverse Events

All SERIOUS ADVERSE EVENTS, regardless of their relationship to study treatment, must be reported on a completed SAE form by email or fax as soon as possible but no later than 24 hours after the investigator becomes aware of the event.

Deaths and life-threatening events should be reported immediately by telephone. The immediate report should be followed up within 1 business day by emailing or faxing the completed SAE form.

Serious adverse events, regardless of causality assessment, must be collected up to 3 months after the last dose of study or through the last visit, whichever is longer. This includes those subjects who discontinue from study drug and who return for regularly scheduled visits where clinical efficacy assessments are conducted. Imaging center personnel should promptly report to the investigator any SAEs which occur while the subject is at the imaging center. (revised per Amendment 01)

For subjects who transition to commercial BAN2401 (including the postmarketing section in Japan), all AEs (including SAEs) will be followed until the end of the study, which will be the date of the last study evaluation prior to transitioning to commercial BAN2401 and at which time all assessments included in Week 261/Early Termination Visit (Part A) and Early Termination Visit (Part B) are to be performed according to the Schedule of Assessments of Part A and Part B, respectively. (revised per Amendment 18 and 19)

All SAEs must be followed to resolution or, if resolution is unlikely, to stabilization. Any SAE judged by the investigator to be related to the study treatment should be reported to the sponsor regardless of the length of time that has passed since study completion.

The detailed contact information for reporting of SAEs is provided in the Investigator Study File.

For urgent safety issues call: [name] (24/7 number). For urgent safety issues, please ensure all appropriate medical care is administered to the subject and contact the appropriate study team member listed in the Investigator Study File.

It is very important that the SAE report form be filled out as completely as possible at the time of the initial report. This includes the investigator's assessment of causality.

Any follow-up information received on SAEs should be forwarded within 1 business day of its receipt. If the follow-up information changes the investigator's assessment of causality, this should also be noted on the follow-up SAE form.

Preliminary SAE reports should be followed as soon as possible by detailed descriptions including copies of hospital case reports, autopsy reports, and other documents requested by the sponsor.

The investigator must notify his/her IRB/IEC of the occurrence of the SAE, in writing, if required by their institution. A copy of this communication must be forwarded to the sponsor or its designee to be filed in the sponsor's Trial Master File.

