At the time of Amendment 11, the Core Study was completed. Preliminary data analysis indicated that the incidence of amyloid-related imaging abnormality edema/effusion (ARIA-E) was less than 10% for the highest BAN2401 dose groups (10 mg/kg biweekly and monthly) and less than 8% overall for subjects receiving treatment with any dose level of BAN2401. There were 5 cases of symptomatic ARIA-E in BAN2401 treatment groups (all developed ARIA-E within the first 12 weeks of treatment): 1 severe ARIA-E on magnetic resonance imaging (MRI) at 2.5 mg/kg biweekly, reported as a non-serious AE; 1 mild ARIA-E on MRI at 10 mg/kg monthly, reported as a serious adverse event (SAE); 1 moderate ARIA-E on MRI at 10 mg/kg biweekly, reported as an SAE; and 2 severe ARIA-E on MRI at 10 mg/kg biweekly, both reported as SAEs. The breakdown of ARIA-E cases by ApoE4 status is provided in [Table 2](#), with the incidence being higher in ApoE4 carriers (<15% at top dose) than non-carriers (8% at top dose). (revised per Amendment 11)

Table 2 Summary of Treatment-Emergent ARIA-E by ApoE4 Status (Safety Analysis Set) (revised per Amendment 11)

Category	Placebo (N=245) n (%)	BAN2401							
		2.5 mg/kg biweekly (N=52) n (%)	5 mg/kg monthly (N=51) n (%)	5 mg/kg biweekly (N=92) n (%)	10 mg/kg monthly (N=253) n (%)	10 mg/kg biweekly (N=161) n (%)	Total BAN2401 (N=609) n (%)		
		ARIA-E	2 (0.8)	1 (1.9)	1 (2.0)	3 (3.3)	25 (9.9)	16 (9.9)	46 (7.6)
		APOE4 positive	2/174 (1.1)	1/38 (2.6)	1/40 (2.5)	3/84 (3.6)	23 ^a /225 (10.2)	7/49 (14.3)	35/436 (8.0)
APOE4 negative	0/71	0/14	0/11	0/8	2/28 (7.1)	9/112 (8.0)	11/173 (6.4)		

APOE4 = apolipoprotein ε4 variant, ARIA-E = amyloid-related imaging abnormality edema/effusion, TEAE = treatment-emergent adverse event

a: One additional ApoE4 positive ARIA-E case was observed after 18 month treatment database lock and after treatment discontinuation; therefore, by definition was not treatment-emergent and is not counted in this table or TEAE description above

After 18 months of treatment in any BAN2401 dose group overall, there were few reported cases of ARIA-E (n=46/609, 7.6%). Most cases of ARIA-E (approximately 61%) occurred within the first 3 months of treatment, were mild to moderate in radiographic severity on MRI, were asymptomatic (92%), and typically resolved within 4 to 12 weeks. (revised per Amendment 11)

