All AEs observed during the study will be reported on the eCRF. All AEs, regardless of relationship to study drug or procedure, should be collected beginning from the time the subject signs the study ICF through the last visit (Visit 43, as shown in [Table 8](#) for the Core Study) (revised per Amendments 08, 09, and 11). SAEs will be collected up to 3 months after the last dose of study drug or through the last visit, whichever is longer. This includes those subjects who discontinue from study drug and who return for regularly scheduled visits where clinical assessments are conducted. (revised per Amendment 01)

For subjects who transition to commercial BAN2401 (including the postmarketing section in Japan), all AEs (including SAEs) will be followed until the end of the study, which will be the date of the last study evaluation prior to transitioning to commercial BAN2401 and at which time all assessments included in Week 261/Early Termination Visit (Part A) and Early Termination Visit (Part B) are to be performed according to the Schedule of Assessments of Part A and Part B, respectively are to be performed. (revised per Amendment 18 and 19)

Abnormal laboratory values should not be listed as separate AEs if they are considered to be part of the clinical syndrome that is being reported as an AE. Any laboratory abnormality considered to constitute an AE should be reported on the Adverse Event eCRF.

It is the responsibility of the investigator to review all laboratory findings in all subjects and determine if they constitute an AE. Medical and scientific judgment should be exercised in deciding whether an isolated laboratory abnormality should be classified as an AE.

Abnormal ECG (QTc) results, if not otherwise considered part of a clinical symptom that is being reported as an AE, should be considered an AE if (1) the QTc interval is >450 ms and there is an increase of >60 ms from baseline, or (2) the QTc interval is >500 ms. Any ECG abnormality that the investigator considers as an AE should be reported as such.

It is the responsibility of the investigator to review the results of the C-SSRS in all subjects and to determine if any of these results constitutes an AE. Medical and scientific judgment should be exercised in deciding whether or not an isolated suicidality rating scale response should be classified as an AE.

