During the Extension Phase, subjects who develop asymptomatic ARIA-H, will continue on the study uninterrupted per the Schedule of Assessments and do not require additional MRI follow-up outside the regularly scheduled assessments. Subjects who develop multiple (>10) asymptomatic cerebral microhemorrhages, superficial siderosis, or a single macrohemorrhage (greater than 10 mm at greatest diameter; also referred to within this protocol as intracerebral hemorrhage >1 cm), will continue on the study uninterrupted per the Schedule of Assessments, and will undertake an unscheduled safety visit (with MRI) at approximately 30 days after the MRI features (asymptomatic ARIA-H) were first identified. Thereafter, all subjects who develop these events will have further safety visits (with MRI) at approximately every 30 days (which may be an unscheduled or a scheduled visit) until the asymptomatic ARIA-H has stabilized radiographically. Subjects who develop symptomatic ARIA-H (including symptomatic microhemorrhages, symptomatic superficial siderosis, symptomatic macrohemorrhage) on MRI will have study drug administration temporarily stopped. All subjects who develop these events will undertake an unscheduled safety visit (with MRI) at approximately 30 days after the MRI features (ARIA-H) were first identified. Thereafter they will have further safety visits (with MRI) at approximately every 30 days (which may be unscheduled or scheduled visit) until the ARIA-H has stabilized and is no longer symptomatic. During treatment interruption, time will elapse on the Schedule of Assessments when the scheduled visit would otherwise occur. They may then resume treatment for the study duration and study assessments remaining on the Schedule of Assessments. Resumption of treatment following symptomatic ARIA-H can only occur twice, after which the subject must be discontinued from the study. (revised per Amendment 12)

Subjects who develop asymptomatic, radiographically mild or moderate Amyloid-Related Imaging Abnormality–Edema/Effusion (ARIA-E) on MRI will continue on the study uninterrupted per the Schedule of Assessments. They will undertake an unscheduled safety visit (with MRI) at approximately 30 days and another safety visit (with MRI) at approximately 90 days (which may be unscheduled or scheduled visit) after the MRI features were first identified. They will continue with study drug treatment if their ARIA-E does not become severe radiologically and remains asymptomatic.

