Moderate ARIA-E: Moderate involvement (area of FLAIR hyperintensity measuring 5 - 10 cm in single greatest dimensions), or more than one site of involvement, each measuring less than 10 cm in a single greatest dimension.

Severe ARIA-E: Severe involvement (area of FLAIR hyperintensity measuring greater than 10 cm in single greatest dimension [white matter and/or sulcal involvement with associated gyral swelling and sulcal effacement]). One or more separate/independent sites of involvement may be noted.

Should a subject discontinue from study treatment from one of these events, such subjects will undergo the Early Termination Visit within 7 days of discontinuation and will undergo the 3 month Follow-Up Visit per protocol. These subjects will continue to be followed with safety MRIs on a monthly basis thereafter, until the finding has either resolved or stabilized.

An end-of-study assessment will be performed for subject who complete treatment in the Extension Phase Part A (Visit 174). Subjects may discontinue from study drug for any reason in the Extension Phase Part A. Subjects who discontinue study drug early are requested to undertake the Early Termination Visit (within 7 days after the last dose of study drug) during which end-of-study assessments will be performed. Any subjects who consent to participation in the PET substudy will have those assessments performed at the Early Termination visit. Subjects who discontinue study drug early may also have unscheduled visits for safety assessments as needed. The Follow-Up Visit will take place 3 months after the last dose of study drug for all subjects. The 3-month Follow-Up Visit is not required for any subject who transitions directly from the Extension Phase Part A (including the postmarketing section in Japan) of the study to commercial BAN2401. For those subjects who transition to commercial BAN2401 (including the postmarketing section in Japan), the end of the study will be the date of the last study evaluation prior to transitioning to commercial BAN2401 and at which time, all assessments included in Week 261/Early Termination Visit are to be performed. (revised per Amendments 15, 17, 18, and 19)

Dosing Regimen Substudy Assessments (revised per Amendment 17)

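### For subjects who transition to commercial BAN2401, the cut-off on AE and SAE follow-up contradicts the SAE resolution rule and the 3-month SAE window, and is not reconciled with the Extension ARIA follow-up rules

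*Protocol*

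**What the plan says.** For subjects who transition to commercial drug, Section 9.5.4.1 sets an end to follow-up: "all AEs (including SAEs) will be followed until the end of the study, which will be the date of the last study evaluation" before transition. Section 9.5.1.5 and the Extension Phase Assessments part of Appendix 4 repeat this. The text is marked as revised by Amendments 18 and 19.

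Other rules on the same events carry no exception for transition:

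- **SAE outcome.** The paragraph after the cut-off in Section 9.5.4.1 reads "All SAEs must be followed to resolution or, if resolution is unlikely, to stabilization".
- **SAE collection window.** Section 9.5.1.5 says "SAEs will be collected up to 3 months after the last dose of study drug or through the last visit, whichever is longer". Section 9.5.4.1 says SAEs "must be collected up to 3 months after the last dose of study or through the last visit, whichever is longer".
- **ARIA.** Appendix 4 requires repeat MRI visits for several kinds of ARIA-H, for the asymptomatic ones "until the asymptomatic ARIA-H has stabilized radiographically". It requires symptomatic or severe ARIA-E to be followed until it resolves. Appendix 5 repeats these rules for Part B.

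The scheduled contact at which such follow-up could happen is removed. Appendix 4 says "The 3-month Follow-Up Visit is not required for any subject who transitions directly from the Extension Phase Part A" to commercial drug, and Section 9.1.3 and Appendix 5 say the same for Part B.

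**The concern.** Two adjacent paragraphs of the SAE reporting section give opposite instructions for an SAE that is unresolved when the subject leaves for commercial drug. One closes follow-up on the exit date. The other keeps it open until the event resolves or stabilizes. The ARIA rules raise the same question: they require further MRI, but the subject's participation has ended and no study visit remains.

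Long-term safety and tolerability is the primary objective of Extension Part A and the only objective of Part B. Commercial availability is a planned way out of both parts. If sites apply the cut-off, the duration and outcome of events open on that date go unrecorded. If they apply the general rules, the outcomes are recorded. If sites differ, completeness of outcome data depends on which paragraph each site followed. Amendment 20 made every intracerebral hemorrhage above 1 cm an SAE, so these events now fall directly within the contradiction, and the cut-off was not revisited when that was done.

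**Working it through.** The protocol gives no figure to reproduce, so the check is mainly a comparison of rules for one subject whose last pre-transition evaluation is on day T.

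1. **SAE open on day T.** The cut-off in Section 9.5.4.1 ends follow-up on T. The next paragraph ends it at resolution or stabilization. These agree only if the event has resolved or stabilized by T. In every other case one rule is broken.

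2. **SAE starting after day T.** The general window runs to 3 months after the last dose or to the last visit, whichever is longer. Take 3 months as 365.25 / 4 = 91 days. Table 16 footnote d (Part B) asks transitioning subjects to attend the Early Termination Visit within 7 days of the last dose. Assume the same interval in Part A, so that T is 0 to 7 days after the last dose. The window then extends past the cut-off by 91 − 7 = 84 days to 91 − 0 = 91 days. Neither Section 9.5.1.5 nor Section 9.5.4.1 says that the cut-off shortens the window.

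3. **ARIA open on day T.** Appendices 4 and 5 require, according to type, MRI visits at about 30 and 90 days, MRI about every 30 days until stable, or follow-up until resolution. None exempts a transitioning subject. But the Synopsis, Section 9.1.3 and both appendices place the end of study for that subject at T, and the 3-month visit is waived. The further rule for monthly MRI after stopping treatment covers subjects who stop because of ARIA. It does not reach a subject who leaves only because commercial drug has become available. The duty remains on paper with no scheduled contact for carrying it out.

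4. **Can a finding first appear on day T?** Table 13 footnote h and Table 16 footnote m require an MRI at the Early Termination Visit if none was done in the preceding 90 days. Part B scans are 6-monthly, about 182 days apart. Assume that exits fall evenly between scans and ignore visit windows. The share of exits needing an MRI is then (182 − 90) / 182 = 92 / 182 = 51%. So an exit MRI is conditional but not rare. This is the share scanned at exit, not the share with a finding.

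5. **Number of subjects affected.** This would need the number who transition, and the rate of SAEs and ARIA open at that time after long exposure. The protocol gives neither.

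**The case against.** The best defence is that the cut-off is a later, specific exception that overrides older general text: the collection rule is marked Amendment 01 and the cut-off Amendments 18 and 19. On this view, post-approval safety reporting takes over once a subject is on commercial drug. That is a reasonable purpose for events that begin after transition. It does not settle events already open. The resolution sentence follows the cut-off and applies to every SAE. Where the sponsor wanted an exception it wrote one: Section 9.5.4.2 says pregnancies conceived after using commercial drug need not be reported, because they are captured as spontaneous reports, and the Follow-Up Visit is waived in terms. Nothing similar is written for open SAEs.

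A second defence is that information can still arrive. Section 9.5.4.1 says any SAE judged related "should be reported to the sponsor regardless of the length of time that has passed since study completion", and that later SAE information received must be forwarded within 1 business day. Both stand. But the first covers only related SAEs, and the second deals with information received; it does not require the site to seek an outcome.

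A reader might infer that ARIA found at the exit MRI gets no follow-up at all. The documents do not support this. The ARIA rules still nominally apply, an intracerebral hemorrhage above 1 cm is an SAE and so falls under the resolution sentence, and some asymptomatic ARIA-H needs no extra MRI in any case. The defect is an unresolved conflict.

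A reader might also size the loss from the statement in Section 7.1.2.3 that ARIA-E cases "were asymptomatic (92%), and typically resolved within 4 to 12 weeks". That figure describes the Core Study, where ARIA-E stopped dosing. In the Extension, asymptomatic mild or moderate ARIA-E (mild only in Japan) continues on study drug, so the time to resolution does not carry over. The same section reports that about 61% of ARIA-E arose in the first 3 months of treatment, which argues against assuming a heavy burden at exit.

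Nor do the documents show that transition is the main way out, or that the loss falls on those with the longest exposure. Table 16 footnote f requires subjects who complete 5 years without transitioning to attend both Visit 174 and the 3-month Follow-Up Visit.

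**Conclusion.** The contradiction is real and lies in adjacent paragraphs of Section 9.5.4.1: for an SAE unresolved at transition, a site cannot follow both. The cut-off also conflicts with the 3-month SAE window, by about 84 to 91 days under the 7-day assumption above, and it is not reconciled with the ARIA rules in Appendices 4 and 5. The consequence is that SAEs and ARIA open at transition, including any first seen on an exit MRI when one is done, may have no recorded outcome. It does not follow that they will have none.

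The number of subjects affected cannot be derived and may be small. The point still merits correction, because it bears on the primary objective of both Extension parts and is cheap to repair. It rests on reading the unqualified SAE sentence as applying to transitioning subjects. If the sponsor meant the cut-off to override it, the text must say so, and known SAEs could then be closed without an outcome by design.

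**What to change.** In Sections 9.5.1.5 and 9.5.4.1 and in Appendix 4, state that for transitioning subjects the date of the last pre-transition evaluation ends collection of new events, as an explicit exception to the 3-month window. State also that SAEs already open on that date, including intracerebral hemorrhage above 1 cm, remain under the existing resolution-or-stabilization sentence. Their outcome would be recorded on the eCRF from available clinical records. The Follow-Up Visit stays waived.

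For ARIA open at transition, the follow-up rules in Appendices 4 and 5 and the matching Synopsis text must be reconciled with the end-of-study date. This review does not say which monitoring rule should apply.

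The cost is outcome queries for subjects with open SAEs, and consistent edits wherever the end-of-study date is restated: the Synopsis, Sections 9.1.3 and 9.5.5, and Appendices 4 and 5. The SAE part needs no new study procedure. Whether the ARIA part does depends on how the sponsor reconciles it.
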